## 1.0 SYNOPSIS

Title:	The Intra-Operative Application of Amiodarone Releasing Hydrogel to Prevent Postoperative Atrial Fibrillation in Patients Undergoing Lung Transplantation
Acronym:	AMGeL
Purpose:	The purpose of the study is to evaluate the intraoperative application of an amiodarone containing hydrogel for prevention of post-operative atrial fibrillation in lung transplant patients.
Objectives:	
Primary Objective: The purpose of the study is to evaluate the intraoperative application of an amiodarone containing hydrogel for prevention of post-operative atrial fibrillation in lung transplant patients.
 
Secondary Objective: Demonstrate safety and effectiveness of the amiodarone hydrogel application during lung transplantation in preventing atrial arrhythmias during first year of transplantation.

Endpoints:	
Primary Endpoint will evaluate: --Development of post-operative atrial fibrillation during initial hospitalization
 
Secondary Endpoints to be evaluated: --Length of Stay initial hospital stay -Development of post-operative atrial fibrillation during first year post transplant -Thirty-day survival -One-year Survival

Design:	
In Lung Transplant patients, we propose use of amiodarone hydrogel during surgery will result in reduced rates of post-op atrial fibrillation.
 
The expected total duration of the study is 24 months.
 
The clinical study will be conducted in 1 center in the United States.
 
20 subjects will be enrolled in this study.
 
The enrolled subjects will be compared to the historical controls who did not receive the amiodarone gel therapy during lung transplant surgery.
 
Subjects will be followed for 1 year.

Drug used:	Amiodarone Hydrogel in Coseal
Study Population	Male and female patients, age 18 years and older with end stage Lung Disease who require Lung Transplant.
Inclusion/Exclusion Criteria	
Inclusion Criteria
 
 
1) Subject or legal representative has signed Informed Consent Form (ICF)
 
2) Undergoing lung transplant at the Jewish Hospital
 
3) Age <math>\geq</math> 18 years
 

	
4) Subjects willing and able to comply with the follow up requirements of the study
 
Exclusion Criteria
 
 
1) Patients with previous history of atrial fibrillation.
 
2) Patients with previously documented allergy or adverse reaction to amiodarone.
 
3) Patients with previous ablation for atrial fibrillation
 
4) Patients with an implantable pacemaker.
 
 
•

Data Collection
	
Subjects will be evaluated and enrolled for receiving the amiodarone gel during their waiting period for lung transplantation.
 
Patients who consent to be part of the study will receive the amiodarone gel during the surgery for lung transplantation. The amiodarone gel will be sprayed just after transplanting the lung(s). Patients will then be followed in-hospital until discharge and data regarding the primary study end-point will be captured.
 
Patient study visit follow-up will occur post-operatively as per standard of care after lung transplantation. Patients' follow-up is generally comprised of routine history and physical examination. These will provide sufficient data to address the secondary study end-points. All follow up data will be collected from the subject's medical records.
 
•

## 2.0 BACKGROUND AND JUSTIFICATION FOR CLINICAL STUDY

Approximately 1900 transplants are performed in the US annually. Lung transplantation remains the gold standard treatment for patients with end stage lung disease. This includes patients with range of etiologies such as Idiopathic Pulmonary Fibrosis, COPD and Cystic Fibrosis. One of the more common post-operative complications in patients undergoing lung transplantation is the development of atrial fibrillation. Recent studies have demonstrated that approximately 1/3 of patients will develop atrial fibrillation during their post-operative course. While it is uncertain if the development of post-operative atrial fibrillation affects survival, it does significantly increase length of hospital stay. Importantly, a portion of the patients that develop atrial fibrillation post-operatively will require cardioversion prior to discharge.

Currently one of the main stays of treatment for post-operative atrial fibrillation is systemic (oral or intravenous) amiodarone, which is a class III antiarrhythmic agent. While this particular drug is effective, it does carry the risk of several known complications. Due to the drug's pharmacokinetics, amiodarone concentrates in organs with high lipid content such as the thyroid, liver and lung. Amiodarone has several known adverse effects on the lung ranging from acute respiratory distress syndrome to more chronic disease such as Interstitial pulmonary fibrosis. Amiodarone can have detrimental effects on the liver which in rare cases could lead to cirrhosis. Additionally, amiodarone can cause thyrotoxicosis as early as a few weeks after the initiation of amiodarone.

The adverse events listed above are related to the cumulative dose of amiodarone. Typically, when amiodarone is initiated, patients receive a loading dose of 600-800mg daily until the cumulative dose reaches 10 grams, after which patients will receive 200mg daily as a maintenance dose. Minimizing the cumulative dose of amiodarone by using a local application, could mitigate the potential adverse drug toxicities. In a previous study, the application of an amiodarone releasing hydrogel performed intraoperatively was shown to significantly decrease the rates of post-operative atrial fibrillation in patients undergoing coronary artery bypass. Currently for patients undergoing lung transplantation, there is not a safe and effective measure available to prevent post-operative atrial fibrillation.

We aim to study the intraoperative application of an amiodarone containing hydrogel for prevention of post-operative atrial fibrillation in lung transplant patients.

In patients undergoing lung transplantation, post-operative atrial fibrillation is common and leads to prolonged hospital course and increased healthcare expenditures. Amiodarone is a main stay of therapy for atrial fibrillation, however this drug does have potential serious complications when administered systemically. The local application of amiodarone, could potentially decrease the rates of atrial fibrillation, while avoiding the systemic complications. This has the potential to decrease length of stay and decrease additional procedures (ie. Cardioversion) in patients undergoing lung transplantation.

### **3.0 RISKS AND BENEFITS OF THE CLINICAL STUDY**

#### **3.1 DESCRIPTION OF SUBJECT POPULATION**

Male and female patients, age 18 years and older with end stage lung disease requiring lung transplantation and are currently on the lung transplant waiting list are the population for this research.

#### **3.2 ANTICIPATED CLINICAL BENEFITS**

Lung transplant patients have approximately 30% risk of developing atrial arrhythmias post-operatively. Currently, there is no preventive treatment strategy to reduce this burden. By conducting this study, we anticipate to demonstrate that amiodarone application through a hydrogel during the surgery is a safe and effective treatment strategy for the prevention of atrial arrhythmias.

#### **3.3 ANTICIPATED ADVERSE EVENTS AND ADVERSE DRUG EFFECTS**

##### **3.3.1 ANTICIPATED ADVERSE EVENTS AND ADVERSE DRUG EFFECTS SECONDARY TO AMIODARONE HYDROGEL APPLICATION**

Currently, the only additional risk incurred by participating in the described in this clinical investigation plan is temporary bradycardia (slow heart rate). In a previous study, by Feng et al, in patients undergoing coronary artery bypass surgery, a similar intervention using amiodarone gel was assessed and the only complication noted in those patients was bradycardia. This complication was temporary and was not clinically significant. In the above study this was a common complication (greater than 10%), however it was not serious and did not require any additional treatment.

If bradycardia is severe enough to be symptomatic, transvenous pacing may be required, in order to maintain a normal heart rate. The risks from this procedure include but are not limited to: death, femoral hematoma, arrhythmias, fever, cardiac tamponade, deep venous thrombosis, and sepsis.

Animal studies and a previous human study did not demonstrate any evidence that the local application of an amiodarone gel to the heart could result in tissue damage. However, tissue damage has been reported if leaks from the vein occur when using intravenous amiodarone

A one-time dose of amiodarone will be used in the preparation of the amiodarone hydrogel. While, the dose used in this study is extremely low, there are several known side effects of amiodarone use, which typically occur when amiodarone is administered systemically for an extended period of time. These potential side effects include: nausea, vomiting, photosensitivity, fatigue, dizziness, paraesthesias, constipation, anorexia, visual disturbances, liver damage, pulmonary fibrosis, hypo or hyperthyroidism, insomnia, headache, sleep disturbances, congestive heart failure, cardiac arrhythmias, SA node dysfunction, abdominal pain, hepatic disorders, flushing, abnormal taste and smell, edema, abnormal salivation and coagulation abnormalities.

##### **3.3.2 ANTICIPATED ADVERSE EVENTS AND ADVERSE DRUG EFFECTS SECONDARY TO LUNG TRANSPLANT**

There are numerous risk to patients undergoing lung transplantation which include but are not limited to: death, hemorrhage, infection, viral infections, arrhythmias, rejection of transplant lung, bronchial anastomotic dehiscence, pulmonary edema, pneumothorax, hemothorax, empyema, pulmonary embolism, post transplant lymphoproliferative disorder, recurrence of primary disease and bronchogenic carcinoma.

#### **3.4 RESIDUAL RISKS ASSOCIATED WITH THE DRUG UNDER INVESTIGATION, AS IDENTIFIED IN THE RISK ANALYSIS REPORT**

Due to the short half-life and one time application of the amiodarone gel, no long term residual risk is anticipated.

### **3.5 RISKS ASSOCIATED WITH PARTICIPATION IN THE CLINICAL STUDY**

The potential risks including anticipated adverse events and possible interactions with amiodarone gel application are expected to be similar to those already reported.

### **3.6 STEPS THAT WILL BE TAKEN TO CONTROL OR MITIGATE THE RISKS**

Mitigations and treatment for all adverse events will be per the current practice standards/standards of care as determined by the investigator. Subject risk from study participation will be mitigated by ensuring that only experienced personnel will be involved in the care of research subjects. The study staff will undergo product, application and study training prior to initiating study activities, and all subjects will be closely monitored throughout the study duration, at pre-specified time points to assess their clinical status.

### **3.7 RISK-TO-BENEFIT RATIONALE**

The potential benefit to patients who undergo the intraoperative application of an amiodarone containing hydrogel at the time of lung transplantation is a reduction in post-operative atrial fibrillation. Currently 1/3 of lung transplant patients develop atrial fibrillation during the post-operative course following lung transplantation. The development of atrial fibrillation significantly increases length of stay and cost of hospitalization for patients following lung transplantation. In a previous study in patients undergoing cardiac surgery, the application of an amiodarone gel significantly reduced the incidence of post-operative atrial fibrillation. The potential benefit of the reduction of atrial fibrillation outweighs the small risk of a transient episode of bradycardia, which was seen in previous studies.

## **4.0 STUDY DESIGN**

### **4.1 PURPOSE**

The purpose of the study is to evaluate the intraoperative application of an amiodarone containing hydrogel for prevention of post-operative atrial fibrillation in lung transplant patients.

### **4.2 STUDY DESIGN AND SCOPE**

This study will prospectively evaluate the use of an amiodarone releasing hydrogel applied to the pulmonary veins and atria at the time of lung transplantation. This study will include patients undergoing lung transplantation at Jewish Hospital, Louisville KY. The prospective group will be compared to historical controls from the same institution. We will access medical records and database entries for those patients undergoing lung transplantation after January 1st 2005 in order to obtain matched controls for analysis. Informed consent will be obtained from the prospective cohort prior to patient enrollment. This pilot study will be used to obtain preliminary data in order to proceed with a larger randomized, controlled trial.

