#### **4.2.3 Number of subjects required to be included in the study**

Enrollment will include at least 20 patients undergoing lung transplant. The subjects will be evaluated with the historic controls (50).

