#### **4.2.4 Estimated time needed to enroll this subject population**

Enrollment is expected to occur over a 24-month period with the total duration of the study continuing up to 30 months, dependent on the rate of enrollment and the regulatory timeline.

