#### 6.2.4 Prior to lung transplant

When a consented subject is informed that they are scheduled for a lung transplant, the study team will review their medical record to confirm they are still eligible to participate in the study. If they meet any of the exclusion criteria since the initial consent was signed, they will be considered a screen failure and will not undergo the study procedure.

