## 14.0 STATISTICAL CONSIDERATIONS

### 14.1 STATISTICAL DESIGN, HYPOTHESES, METHOD AND ANALYTICAL PROCEDURES

This clinical study will provide data to support the safety, preliminary efficacy, and performance of the use of the Amiodarone hydrogel in preventing atrial arrhythmia during lung transplantation. The study has a treatment arm and a control arm. The control arm is the historic controls and will use the previously treated lung transplant patients at the facility. The treatment arm will use investigational amiodarone hydrogel. The study sample size calculation is based on typical regulatory criteria for a feasibility study to assess for safety and preliminary effectiveness hence it is not based on a power analysis to show statistically significant difference between the groups. However, the reported rate of early atrial fibrillation post lung transplantation is approximately 30% and assuming that the use of amiodarone gel will result in prevention of atrial fibrillation in 90% patients a sample size of 20 in each arm may have sufficient power to answer the question of preliminary effectiveness and safety.

Endpoint analysis will be on “as-treated” basis as historical control data will be used. Patients who will dropout or withdraw from the study before reaching the primary end-point will be excluded from the study and replaced by new enrollees to have at least 20 patients enrolled the study arm. The primary end-point analysis will be based on the study groups as per the protocol (treatment group vs. control groups). Subjects, who withdraw consent, will not be included in analyses.

All clinically relevant baseline and follow up variables will be tabulated. Means, medians, proportions and 95% confidence intervals will be reported. Comparisons of data collected at baseline and at follow-up will be analyzed as follows: categorical variables will be tested using contingency tables analyses (exact or chi-square approximations), and continuous variables will be tested using unpaired Student’s t-test or Wilcoxon rank-sum test, depending on variable distribution. The post-transplant AFIB was evaluated between study and control groups for overall occurrence, AFIB lasting < 24 hours and AFIB lasting > 24 hours. All the data were analyzed using SAS 9.4 software (SAS Inc., Cary, NC).

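### The control window opens in 2005 with no closing date, selection rule or adjustment for transplant year, so every gel-versus-control comparison may be confounded by era.

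*Combined protocol and SAP*

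**What the plan says.** Section 4.2 states that "The prospective group will be compared to historical controls from the same institution", and that records will be searched for "patients undergoing lung transplantation after January 1st 2005 in order to obtain matched controls for analysis". This is the only place that dates the control window or mentions matching. The matching variables, ratio and method are not given.

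Section 4.2.3 sets the numbers: "Enrollment will include at least 20 patients undergoing lung transplant", and "The subjects will be evaluated with the historic controls (50" in total. How the 50 are chosen from the window is not stated.

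The Synopsis describes the comparators as "historical controls who did not receive the amiodarone gel therapy during lung transplant surgery". Section 14.1 adds: "The control arm is the historic controls and will use the previously treated lung transplant patients at the facility". The same section plans contingency-table tests for categorical variables and unpaired t-tests or rank-sum tests for continuous ones, with no stratification or covariate.

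On timing, section 4.2.4 says "Enrollment is expected to occur over a 24-month period with the total duration of the study continuing up to 30 months", and Appendix B dates the first draft 06/06/17. The demographic case report form in Appendix E has a field for transplant date. The eligibility criteria in section 4.5 are written for participating subjects and are not said to apply to controls.

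**The concern.** With historical controls, the gel effect and the effect of calendar time cannot be separated unless the plan restricts, matches or adjusts for time. This plan states none of these. Length of stay, 30-day survival and one-year survival plausibly depend on the standard of care at the time of transplant. AF incidence and its detection may also change over the years, and the primary endpoint uses the same 50 controls, so it is exposed as well.

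There is a second, related gap. Control outcomes are already in the records when the 50 are picked, and no rule fixes the order of selection. Two analysts working in good faith could assemble different control groups from the same window and reach different conclusions.

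Section 4.2 says the pilot is to inform a larger randomised trial. An era artefact would therefore carry into the effect size assumed for that trial.

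**Working it through.** The plan gives no figure for era differences, so there is nothing of its own to reproduce. The check has two parts: what the text fixes, and how large the distortion could be under stated assumptions.

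**1. Length of the window.** From 1 January 2005 (section 4.2) to 6 June 2017 (Appendix B) is 12 years and 5 months, about 12.4 years. Section 8.1 bars enrolment before FDA and IRB approval, so gel patients come after that date. If the window were never closed, 24 months of enrolment would bring it to about 12.4 + 2 = 14.4 years.

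**2. What controls for time.** Restriction: a start date only. Matching: the word appears, with no variable named. Adjustment: none in section 14.1. Order of selection: none stated.

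**3. AF, drift favouring gel.** Inputs from the plan: 20 gel patients and 50 controls (section 4.2.3) and an exact or chi-square test (section 14.1). Assumed: two-sided 0.05, an inert gel, a current AF rate of 25%, and early controls at 35% or 40%. These rates lie on either side of the approximately 30% quoted in section 14.1.

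If a share s of the controls is early, the average control rate is pC = (1 − s) × 25% + s × early rate. For s = 0.5 this gives 0.5 × 25 + 0.5 × 35 = 30% and 0.5 × 25 + 0.5 × 40 = 32.5%.

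The chance of a significant result favouring gel is the sum, over all x of 50 and y of 20, of Bin(x; 50, pC) × Bin(y; 20, 25%), counting only tables with two-sided Fisher p<0.05 and x/50 > y/20. The controls are treated as one binomial at the average rate.

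| Controls | pC | Gel | Chance favouring gel |
|---|---|---|---|
| No drift | 25% | 25% | 1.2% |
| Half early, at 35% | 30% | 25% | 3.7% |
| Half early, at 40% | 32.5% | 25% | 5.8% |
| All early, at 35% | 35% | 25% | 8.7% |
| All early, at 40% | 40% | 25% | 17.0% |

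The right comparator is 1.2%, the actual rate of this conservative test with no drift, and not the nominal 2.5%.

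**4. AF, drift against gel.** Suppose the gel truly lowers AF from 30% to 10%. With controls at the current 30%, the same calculation gives a 33.3% chance of significance. If the controls came from a period with AF at 20% (assumed), it falls to 6.9%.

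**5. Other endpoints, inert gel.** One-year mortality, with current patients at 15% (assumed): controls at 15%, 20%, 25% and 30% give 0.5%, 2.6%, 7.7% and 17.4%. Length of stay, normal approximation: the standard error in SD units is √(1/50 + 1/20) = 0.265. A control stay longer by 0.25 SD gives Φ(0.25/0.265 − 1.96) = 15.5%, against 2.5% with no drift.

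**The case against.** The strongest reply is that this is a pilot whose sample size is expressly not based on power, and that section 4.2 does say the controls will be matched. The 50 could all be recent, and year could be one of the matching factors. This stands in part: the documents support the statement that era *may* confound the comparisons, not that it will. A reader might infer that transplant date plays no part in choosing the controls, but the text is silent on this. The pilot label does not close the gap, because section 14.1 still plans formal between-group tests and speaks of preliminary efficacy.

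It is also fair that every drift size above is assumed, that the larger AF figures need all 50 controls to be early, and that drift can run against gel. Outcomes are on record for any retrospective control group. That is a reason to fix the selection rule in advance, not a defect peculiar to this plan.

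A reader might go further and infer that patients transplanted during the study without gel could be used as controls. Section 6.2.4 says of those who become ineligible that "they will be considered a screen failure and will not undergo the study procedure", and no sentence excludes them from the control group. The documents do not support that inference. The controls are called historical throughout, and section 14.1 describes them as previously treated, which plainly points to patients transplanted before the study. No passage assigns screen failures or decliners to the control group. A clarifying sentence is useful, but nothing here depends on it.

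**Conclusion.** The point holds as a gap in control selection. The window has a start and no end, the matching is unspecified, and the tests take no account of transplant year. AF in hospital and over the first year, length of stay, and 30-day and one-year survival are all exposed, in either direction.

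Under the assumed AF rates, an inert gel would look significantly better in 3.7% to 17.0% of such studies, depending on how many controls are early, against 1.2% without drift. Opposite drift could cut the chance of detecting a true 30% to 10% reduction from 33.3% to 6.9%. These figures illustrate sensitivity and do not estimate bias, since the documents contain no survival rate, length of stay or time trend by year. The gap itself can be read directly from sections 4.2, 4.2.3 and 14.1 and does not rest on those assumptions. It should be corrected before controls are chosen.

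**What to change.** In sections 4.2 and 4.2.3:

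- Close the control window before the first gel application.
- Apply the study eligibility criteria in section 4.5 to controls, as far as the records allow.
- Select controls before their outcomes are abstracted, in one of two ways: the 50 most recent consecutive eligible transplants, working backwards; or, if matching is kept, matching on named factors that include transplant year.
- Add, as a clarification only, that patients approached or consented for this study are not controls.

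The cost is wording. The number of charts stays at 50, and transplant date is already on the case report form. The downside is a smaller pool for matching on other characteristics. Era differences are reduced, not removed: if the centre's eligible volume were close to planned accrual (an assumption; 20 in 24 months), 50 consecutive controls would span 50/20 × 24 = 60 months, or five years.
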